Our long-term goal is to understand how to change anomalous cognitive processes underlying OCD and its related conditions such as trichotillomania (TTM) in order to develop and disseminate effective computer-based cognitive interventions. The objective of the current R21 application is to examine the feasibility of using a computerized RI training (RIT) program to improve OCD-related symptoms. Our central hypothesis is that cognitive training designed to enhance RI will improve this problematic cognitive process in OCD and TTM and produce a significant reduction in OCD/TTM symptoms. This hypothesis is based on (a) existing behavioral, electrophysiological, and neuroimaging data suggesting poor RI as a core feature of OCD and TTM and (b) our preliminary data suggesting that RIT can be a useful therapeutic intervention for OCD and its related conditions characterized by poor RI. The expected results will lay a strong groundwork for future studies at the R01 level aimed at developing, testing and disseminating evidence-based RI-focused cognitive training for OCD that can be used as an adjunctive intervention to enhance existing treatments or as a stand-alone intervention. We propose two specific aims and an exploratory aim for this proposal.

Aim 1. To determine the effectiveness of computerized RIT in enhancing RI among OCD/TTM patients.

We hypothesize that OCD/TTM patients who undergo the 8-session RIT program will show greater RI capabilities, relative to OCD/TTM patients who receive placebo cognitive training.

Aim 2. To determine the utility of computerized RIT in improving OCD/TTM symptoms. We hypothesize that OCD/TTM patients who undergo the 8-session RIT program will show a greater reduction in OCD/TTM symptoms, relative to OCD/TTM patients who receive placebo cognitive training.

Exploratory Aim. To evaluate the subjective treatment experiences and patient retention. To assess the end-user acceptability of the proposed cognitive training program, we will assess treatment acceptability and satisfaction as well as treatment refusal and drop-out rates.

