Participants. We will recruit 30 individuals who meet the following inclusion criteria: (a) age between 18 and 60, (b) a primary diagnosis of OCD/TTM as determined by the Structured Clinical Interview for DSM-5 (SCID-5), (c) moderate level of OCD or TTM symptoms,⁴⁷ and (d) IQ > 80 (on the Wechsler Abbreviated Scale of Intelligence-II). Exclusion criteria include: (a) current substance abuse/dependence, (b) current or past psychotic disorder, bipolar disorder, or schizophrenia, (c) presence of ADHD, or TS (conditions known for poor RI), (d) severe depressive symptoms (evidence suggests that executive function deficits in OCD are attributable to comorbid depression^{48,49}), (e) current psychotherapy, (f) current psychoactive medications (a variety of pharmacological agents were shown to be implicated in RI, including dopamine, norepinephrine, and serotonin⁵⁰⁻⁵²), and (g) current suicidality.

Cognitive Training Programs. RIT is a 30-level computer game (with a story of defending a village from aliens), designed to offer systematic practice of RI focused primarily on action withholding and cancellation, incorporating parameters of go/no-go and stop-signal tasks. Main task materials are simple geometric figures (e.g, squares, circles). However, RIT is different from a mere repetition of existing go/no-go or stop-signal tasks in several important ways: (a) with ascending levels, RIT becomes more difficult by systematically varying RI

task parameters integrated into each game level (i.e., frequencies of no-go or stop trials, stop-signal latencies, and increased stimulus potency via set switching); (b) RIT guides participants to make individually-tailored progress toward their own levels of challenge (i.e., each level is repeated until high accuracy is reached); (c) RIT contains video-game features to maximize participant's motivation (e.g., engaging story and graphics, and display of record scores); and (d) RIT provides trial-by-trial performance feedback to help participants make conscious efforts to improve their ongoing performance. In each 45-min session, five 7-min game levels are offered with brief inter-level breaks. After completing each level, a result page will summarize the participant's performance. The central training components of RIT are the same as those used in our pilot studies.

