We will also use the stop-signal and go/no-go task, in which participants should promptly indicate the direction (left vs. right) of an arrow on each trial, but inhibit response when an auditory stop signal is presented. Stop Signal Reaction Time (SSRT; time taken to complete the inhibitory process) is estimated using the tracking algorithm, which adjusts the stop signal delay automatically (by 50ms) to maintain the rate of successful inhibition on stop-signal trials at 50%.¹⁰ This particular version has successfully demonstrated the RI deficits in both OCD patients and unaffected first-degree relatives.^{7,43} The SSRT is a behavioral RI outcome measure for this study. The go/no-go task asks participants to quickly press a button for letters (e.g., Q, P, T; go trials) except to the letter X (no-go trial).⁶⁷⁻⁶⁹ Twenty-five percent of the task constitutes no-go trials. The RI index from this task is the number of commission errors. Patients with OCD showed abnormal activity in fronto-striatal circuits while performing this type of go/no-go task.^{35,69}

STATISTICAL ANALYSIS PLAN

Power Analysis. We conducted power analyses using a conventional large effect size ($f = .40$). With $\alpha = .05$, a correlation of .5 among repeated measures, and a nonsphericity correction of .6, the required sample size is 9 per group to achieve the power of .80 in detecting a large group X time interaction effect ($f = .40$). Based on the recommendation from Ukoumunne et al.⁷⁰ that allows standard power analyses to be used for

multilevel models by multiplying the sample size by the design effect, the necessary sample size is 20 after an adjustment by a factor of 1.1, which was derived from an assumed intraclass correlation of .05. Taking into account 25% patient attrition ($n=5$), a total of 25 would offer an adequate sample size to detect a medium to large effect size. Thus, this proposal ($N=30$) is sufficiently powered ($=.90$) to detect a large effect, but is underpowered ($=.50$) to detect a medium effect ($f=.25$).

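### The power paragraph calls a total of 25 adequate for a medium to large effect, but 25 was sized only for a large effect (f = .40), and its attrition step is two patients short

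*Combined protocol and SAP*

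**What the plan says.** All of this is in the Power Analysis paragraph of the Statistical Analysis Plan unless noted.

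- The effect size used is f = .40, labelled large. With alpha .05, "a correlation of .5 among repeated measures, and a nonsphericity correction of .6, the required sample size is 9 per group" for power .80 on the group-by-time interaction.
- The multilevel adjustment follows: "the necessary sample size is 20 after an adjustment by a factor of 1.1, which was derived from an assumed intraclass correlation of .05".
- The attrition step reads "Taking into account 25% patient attrition ($n=5", and the sentence concludes that "a total of 25 would offer an adequate sample size to detect a medium to large effect size".
- The next sentence states that "this proposal ($N=30$) is sufficiently powered ($=.90$) to detect a large effect, but is underpowered ($=.50$) to detect a medium effect". It gives the medium effect as f = .25.
- The Participants section sets the number actually planned: "We will recruit 30 individuals who meet the following inclusion criteria". The Project Overview splits this 15 and 15.

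**The concern.** The paragraph fixes its own labels: f = .25 is medium and f = .40 is large. Two adjacent sentences then disagree. If 30 is underpowered for a medium effect, 25 cannot be adequate over a range that starts at medium. Nothing in the chain from 9 per group to 20 to 25 uses any effect other than f = .40.

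The attrition step has a separate slip. It adds 25% of 20, whereas a 25% loss applies to the number enrolled.

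The stake is the accuracy of the only sample-size justification in the documents. The protocol says that "The expected results will lay a strong groundwork for future studies at the R01 level". A reader who carried the figure of 25 into later planning would take with it a sensitivity that the plan itself denies.

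**Working it through.** **Inputs.** From the Power Analysis paragraph: alpha = .05, correlation rho = .5, nonsphericity epsilon = .6, target power .80, f = .40 and f = .25, factor 1.1, attrition 25%. From Specific Aim 1 in the SAP: m = 3 time points. From the Project Overview: k = 2 equal groups.

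**Formula.** The plan prints none. I used the standard noncentral F for a repeated-measures group-by-time interaction:

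- lambda = f² × N × m × epsilon / (1 − rho) = f² × N × 3 × .6 / .5 = 3.6 × f² × N
- df1 = (k − 1)(m − 1) × epsilon = 1.2
- df2 = (N − k)(m − 1) × epsilon = 1.2 × (N − 2)

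**Step 1: reproduce the plan's figures.**

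- At f = .40, N = 16 gives lambda = 9.216 and power .789. N = 18 gives lambda = 10.368 and power .841. So 9 per group reproduces.
- 18 × 1.1 = 19.8, rounded to 20. This reproduces.
- For N = 30 the plan does not say what is netted out, so I tried the candidates against its .90 and .50:

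| Treatment of N = 30 | Net N | Power, f = .40 | Power, f = .25 |
|---|---|---|---|
| 25% attrition and 1.1 | 30 × .75 / 1.1 = 20.45 | .889 | .506 |
| 25% attrition only | 22.5 | .919 | .549 |
| Factor 1.1 only | 27.27 | .962 | .640 |
| No adjustment | 30 | .976 | .685 |

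The first row comes closest to the stated pair and is taken as the plan's likely basis.

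**Step 2: apply the same calculation to 25.**

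| Treatment of N = 25 | Net N | Power, f = .25 | Power, f = .40 | Smallest f with power .80 |
|---|---|---|---|---|
| 25% attrition and 1.1 | 25 × .75 / 1.1 = 17.05 | .428 | .818 | .391 |
| Lose exactly 5, then 1.1 | 20 / 1.1 = 18.18 | .454 | .845 | .377 |
| 25% attrition only | 18.75 | .468 | .858 | .370 |
| Factor 1.1 only | 22.73 | .554 | .922 | .333 |
| No adjustment | 25 | .598 | .945 | .316 |

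Power at f = .25 never exceeds .60.

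**Step 3: attrition.**

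- The plan's step: 20 + .25 × 20 = 25.
- Check: 25 × .75 = 18.75, which is below 20. Losing 5 of 25 is 20%, not 25%.
- Correct inflation: 20 / .75 = 26.7, so 27, or 28 for equal arms. Check: 27 × .75 = 20.25.
- Planned enrolment: 30 × .75 = 22.5, which is above 20.

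**The case against.** The strongest reply is that nothing operative rests on 25. The planned number is 30, and the very next sentence discloses low power for a medium effect. This stands, and it is why the point is minor. It does not remove the error, because two incompatible statements remain side by side.

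A second reply is that *medium to large* may mean somewhere between the two. If 25 is not netted down at all, power at the midpoint f = .325 is .82. But the sentence itself says that attrition has been taken into account, and with both adjustments power at f = .325 is .64. The loose reading works at the midpoint only if both of the plan's adjustments are dropped.

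Third, the netting basis is inferred, so .43 and .39 are the least favourable of the readings and are not the plan's own printed figures. This stands, and the range is therefore given. The conclusion holds across all of it.

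Fourth, on attrition: the plan prints the loss as 5, and 25 − 5 = 20 agrees with itself. Moreover, 25 still meets the .80 target at f = .40 after a true 25% loss (.818; 24 enrolled would give .799). This also stands. The shortfall is against the plan's rounded-up 20, not against its power target, and it amounts to two patients.

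**Conclusion.** The sentence is wrong as written, and the point is minor. A total of 25 supports a large effect (power .82 at f = .40 after both adjustments) but not a medium one (.43 to .60 at f = .25). Power .80 is reached only from f = .32 to .39, depending on the reading. The attrition step is a secondary slip of two patients: 25 where 20/.75 gives 27.

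A reader might infer that the trial is too small for its stated aim, or that the .90 and .50 at N = 30 are mistaken. The documents support neither. The planned 30 leaves 22.5 after 25% attrition, and .90/.50 reproduce approximately (.889/.506). Nor can one infer that low power for a medium effect was hidden, since the plan states it.

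These figures rest on the repeated-measures F test with three time points as the basis of the plan's power calculation, and the .43 and .82 also on netting out both attrition and the 1.1 factor. The SAP's planned analysis is a multilevel model with a condition-by-time slope, so they check the power paragraph's consistency and are not a power calculation for that model. The contradiction between the two sentences and the attrition arithmetic need no such assumption.

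**What to change.** Replace the one sentence with wording such as:

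*Allowing for 25% attrition (20/.75 = 26.7), enrolling 27 patients (28 for equal arms) is adequate to detect a large effect (f = .40).*

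This removes the claim about medium effects and corrects 25 to 27. Keep N = 30 and the stated .90 and .50.

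The cost is one sentence of SAP wording. No extra patients are needed, since 27 or 28 is below the planned 30, and the design and analysis stay as they are. The downside is that the stated adequacy becomes slightly less favourable.

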Similar to other cognitive retraining paradigms, the RIT is based on the rationale that repeated practice of the core cognitive process central to the condition would result in clinically meaningful improvement. The RIT is expected to allow individuals to practice (a) suppressing pre-potent stimulus-response association, (b) inhibiting potent ongoing response, (c) selectively inhibiting response to inappropriate stimuli, (d) exerting cognitive flexibility to changing targets, and (e) maintaining goal-directed responses in the given context. Based on the evidence suggesting RI as a core feature of OCD and our preliminary data, we predict that RIT will generate meaningful clinical improvement in OCD beyond a simple task practice effect which would improve only RI task performance without affecting OCD symptoms.

Similarly, PLT is a 30-level computer game but presents only go trials, and thus provides no opportunity to practice RI components (i.e., action withholding and cancellation). However, its 30-level structure and task stimuli are identical to those of the RIT program, and they also become increasingly difficult across level (by more abrupt onsets and increasingly shorter duration of the stimuli). We expect PLT to have negligible effects on RI capabilities and OCD symptoms. The RIT/PLT will be administered in a small therapy room at the UWM Psychology Clinic and Anxiety Lab. The participant will complete each training session following the computerized instructions. A trained administrator will be present in all sessions to assist in the event of any technical difficulties.

Primary and Other Outcome Measures

Considering the inclusion of two diagnostic conditions (OCD and TTM), we will obtain clinician-rated symptom ratings for both conditions, using the Yale-Brown Obsessive-Compulsive Scale and the NIMH TTM Symptom Severity Rating Scale. The primary outcome index will be a z-transformed score of the symptom ratings obtained from the two rating scales. We will also use the Clinical Global Impression (CGI) rating scale is a widely used brief assessment tool for evaluating illness severity, global improvement or change, and therapeutic response.

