Specific Aim 1 - To determine the effectiveness of RIT in enhancing RI among OCD/TTM patients. To attain the objective of Aim 1, we will test the working hypothesis that RIT will show greater improvement in RI performance than PLT. Our primary analytic strategy is multilevel modeling, which effectively handles multi-session data with hierarchical structure (i.e., three time points nested in individuals), missing data, and serial correlation. To test the hypothesis, the level-1 intercept will be regressed on training condition to examine group differences, and the slope for time will be regressed on training condition to produce a cross-level interaction to examine the differential rate of change in RI performance between the two groups.

Specific Aim 2 - To determine the utility of the RIT in reducing OCD/TTM symptoms. To attain this objective, we will test the working hypothesis that RIT will show a greater reduction in OCD/TTM symptoms than PLT. Our primary analytic strategy is random effects mixed model analyses, in which the level-1 intercept will be regressed on training condition to examine group differences and the slope for time will be regressed on training condition to produce a cross-level interaction that examines group differences in the rate of change in OCD/TTM symptom z-scores.

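### Does Aim 1 need a rule saying whether SSRT, commission errors or a composite decides it?

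*Combined protocol and SAP*

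**What the plan says.** The SAP, under Specific Aim 1, states one hypothesis: "we will test the working hypothesis that RIT will show greater improvement in RI performance than PLT". The test is the cross-level interaction of training condition with time, used "to examine the differential rate of change in RI performance between the two groups". No task or index is named there.

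The outcome-measures section supplies two candidates. For the stop-signal task: "The SSRT is a behavioral RI outcome measure for this study". For the go/no-go task: "The RI index from this task is the number of commission errors". Neither is called the lead, and there is no composite, no either-or-both rule and no multiplicity adjustment. The Project Overview counts three response-inhibition tasks at baseline, while this section describes two.

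Aim 2 does name its variable. It tests "group differences in the rate of change in OCD/TTM symptom z-scores", and the outcome section makes a z-transformed symptom rating the primary outcome index.

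The Power Analysis concerns a generic group-by-time interaction and says that N = 30 "is sufficiently powered ($=.90$) to detect a large effect, but is underpowered ($=.50$) to detect a medium effect" (f = .25).

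**The concern.** Aim 1 is one of the two specific aims, not the exploratory one, and is worded as a single hypothesis with a single test. With two unranked indices the verdict is clear only when they agree. If SSRT improved and commission errors did not, or the reverse, an analyst could claim support because one index was positive or deny it because one was not, and could make that choice after seeing the data. The stated power belongs to one test, and the plan does not say which Aim 1 variable that test uses.

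The choice has content. The training offers "systematic practice of RI focused primarily on action withholding and cancellation"; the stop-signal task measures cancellation and the go/no-go task withholding, so relying on one index drops part of what is trained. The protocol also contrasts the predicted clinical benefit with "a simple task practice effect which would improve only RI task performance without affecting OCD symptoms", which seems to call for a clear finding on whether response inhibition improved.

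**Working it through.** **Inputs from the Power Analysis and Aim 1 text.** α = .05; two groups; m = 3 time points; correlation ρ = .5; nonsphericity ε = .6; f = .40 or .25; N = 30; attrition 25%; design effect 1.1.

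**Step 1: reproduce the plan's figures.** Noncentral F for the group-by-time interaction: λ = f²·N·m·ε/(1 − ρ), df1 = (m − 1)ε = 1.2, df2 = (N − 2)(m − 1)ε.

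- N = 18, f = .40: λ = .16 × 18 × 3 × .6/.5 = 10.37, df2 = 19.2, power .841. N = 16 gives .789. So 9 per group is the smallest equal-arm size reaching .80, as stated. 18 × 1.1 = 19.8, rounded to 20, also as stated.
- Effective N at the planned size: 30 × .75/1.1 = 20.45, df2 = 22.15. At f = .40, λ = 11.78 and power is .889 (stated .90). At f = .25, λ = 4.60 and power is .506 (stated .50).

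The plan's figures are therefore the power of one test.

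**Step 2: two indices.** Assumptions not in the documents: each index has the Step 1 power, the effects are equal, and the two test statistics are bivariate normal with correlation r. The mean shift giving .889 at two-sided .05 is 3.184; for .506 it is 1.974. P(both) = 2p − P(either), and P(split) = P(either) − P(both).

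| f | r | Either | Both | Split |
|---|---|---|---|---|
| .40 | 0 | .988 | .791 | .197 |
| .40 | .5 | .963 | .816 | .146 |
| .40 | .8 | .937 | .842 | .094 |
| .25 | 0 | .756 | .256 | .500 |
| .25 | .5 | .672 | .339 | .333 |
| .25 | .8 | .608 | .403 | .205 |

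At the effect the plan is powered for, a split is a clear minority outcome. At f = .25 it reaches one half only when the statistics are independent.

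**Step 3: sensitivity to the form of the test.** Aim 1 tests a slope, which is a single-degree-of-freedom contrast needing no sphericity correction. With λ = f²·N·m/(1 − ρ) at N = 20.45 and purely linear change, power is .987 (f = .40) and .746 (f = .25). If change is complete by post-training and then holds, the linear contrast captures three quarters of λ, and power is .953 and .623. Independent splits, 2p(1 − p), are then 2.5% and 9.0% at f = .40, and 37.9% and 47.0% at f = .25. The Step 2 figures are illustrative.

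**Step 4: false support under no effect.** The hypothesis is directional, so only results favouring the training can support it. One two-sided .05 test gives .025. For two tests, P(either favourable) = .05 − P(both favourable):

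- r = 0: .05 − .0006 = .0494
- r = .5: .05 − .0046 = .0454
- r = .8: .05 − .0110 = .0390

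Counting rejections in either direction gives 9.75% to 7.8%, but about half of those favour placebo training.

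**Step 5: what a rule would buy.** A standardised mean of the two indices has effect f√(2/(1 + r)) when both respond equally. Power is then .92–.995 at f = .40 and .55–.80 at f = .25. If only one index responds, at f = .40, the effect is f/√(2(1 + r)) and power falls to about .38–.61. Holm over the two gives a particular index .85–.88 and .43–.44. One named index keeps .89 and .51 but leaves the other component out. No option is better in every case.

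**The case for a change.** The strongest case for a change is that reporting both indices does not settle the single hypothesis when they disagree, and that the unwritten rule matters. At f = .25, Aim 1 would be called supported with probability .61–.76 if either index suffices, .26–.40 if both are needed, and .51 for one named index. A sentence would cost nothing in data or patients, and Aim 2 shows that the investigators could name a variable.

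The omission and the arithmetic stand. What does not follow is that the plan leads to a wrong result. It states no faulty rule; it gives a model and two defined indices. Both interaction estimates with their intervals are valid whatever label is put on Aim 1, and a split shown openly is informative, since it would suggest that one component responded to training and the other did not. The spread above is largest at an effect for which the plan already calls itself underpowered.

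The comparison with Aim 2 is also weaker than it looks. Its z-score exists because two diagnoses are enrolled, and how the two scales combine is not spelled out either. The contrast with a practice effect turns mainly on whether symptoms improve, which is Aim 2's question. The count of three tasks against two described is a mismatch in description and does not alter the analysis of the two defined indices.

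**Conclusion.** No change follows. The plan leaves unsaid which index decides Aim 1, and analysts can fill that gap sensibly by fitting the stated model to SSRT and to commission errors and reporting both. The trial is a 30-patient feasibility study whose primary outcome is the symptom z-score, and that outcome is unaffected.

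The size is modest where the plan claims adequate power: a split in about 9–20% of trials at f = .40, rising to 20–50% at f = .25. These ranges assume equal effects, the plan's stated power for each index and a correlation of 0 to .8 between test statistics, none of which the documents establish for these two tasks. The worst inflation, if one positive index were treated as enough without adjustment, takes false support from 2.5% to 3.9–4.9%. Choosing among a composite, Holm and a single index trades coverage of both components against power, and the documents do not settle that choice.

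### Both mixed models leave each arm its own baseline mean; if allocation is random, a common baseline mean could make the condition × time slope more precise, by an amount the plan does not fix

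*Combined protocol and SAP*

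**What the plan says.** Under Specific Aim 1 of the Statistical Analysis Plan, "the level-1 intercept will be regressed on training condition to examine group differences, and the slope for time" is likewise regressed on condition; the resulting cross-level interaction tests the hypothesis. The data are "three time points nested in individuals": baseline, post-training and 1-month follow-up. Specific Aim 2 repeats this model for the symptom z-scores: "Our primary analytic strategy is random effects mixed model analyses", "in which the level-1 intercept will be regressed on training condition to examine group differences". Neither aim includes a baseline covariate or a common baseline mean.

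Several features that decide how much baseline could contribute are left open:
- **Covariance.** Aim 1 says the method handles "missing data, and serial correlation", but no structure is named, and neither aim says whether slopes are random.
- **Power inputs.** The Power Analysis uses "a correlation of .5 among repeated measures, and a nonsphericity correction of .6". These are inputs to the sample size, not a specification of the analysis model.
- **Entry rule.** Participants need a "moderate level of OCD or TTM symptoms", which may narrow the spread at baseline.
- **Outcome scale.** The primary index is a "z-transformed score of the symptom ratings obtained from the two rating scales". The text does not say whether it is standardised by visit or over all visits.
- **Time coding and allocation.** How time is coded is not given. The Project Overview gives 15 per arm and describes blinding, but the supplied text does not say that allocation is random.

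**The concern.** A free intercept and a free slope in each arm leave both fitted baseline means unconstrained, whatever the time coding. With complete, equally spaced visits under compound symmetry, the slope contrast is then half the arm difference in follow-up minus baseline, which is a raw change score. Chance imbalance at baseline therefore passes straight into the estimated slope difference. Under random allocation any baseline difference is chance, and a model that says so can remove part of that noise.

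The plan puts its own power at .50 for a medium effect with 30 participants. A baseline score that is collected anyway is a cheap place to look for precision, and Aim 2 concerns the primary outcome.

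A smaller matter is the intercept term, which the plan includes to look at group differences. If time 0 is baseline, that term is the arm difference before training and carries no information on efficacy.

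**Working it through.** **1. The plan's own power figures.** Inputs from the Power Analysis: α = .05, ρ = .5, ε = .6, f = .40 or .25, design effect 1.1, attrition 25%. There are k = 2 arms and m = 3 visits. For an omnibus group × time F test:

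λ = f²·N·m·ε/(1−ρ), df1 = (k−1)(m−1)ε = 1.2, df2 = (N−k)(m−1)ε.

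- N = 18, f = .40: λ = .16 × 18 × 3 × .6/.5 = 10.37 and power is .841. N = 16 gives .789, so 9 per group reproduces.
- 18 × 1.1 = 19.8, or 20 in total.
- N = 30 × .75/1.1 = 20.45: power is .889 at f = .40 (stated .90) and .505 at f = .25 (stated .50).

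The stated .50 is therefore the power of an omnibus interaction with a nonsphericity correction, not of the 1-df slope test in the analysis section.

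**2. Slope variance, free against common baseline.** Assumptions: times 0, 1, 2 (4 weeks of training, then about a month to follow-up), 15 per arm, generalised least squares, equal variances of 1, compound symmetry.

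- Free intercept: variance = 2 × [2(1−ρ)/4]/15 = (1−ρ)/15 = .0333 at ρ = .5.
- Common baseline: variance = (2/15)/(t′V⁻¹t). At ρ = .5, V⁻¹ = 2I − .5J, so t′V⁻¹t = 2 × 5 − .5 × 9 = 5.5 and the variance is .0242.
- Fractional cut = .5(1−ρ)/[ρ + (5/6)(1−ρ)] = .25/.9167 = 27%.

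With assumed dropout per arm of 11 with three visits, 2 with two and 2 with one, the variances are .0415 and .0317, a 24% cut. Two other dropout patterns give 22% and 26%.

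**3. Other covariances (complete data).** The random-slope rows assume intercept and residual variance .5.

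| Assumed covariance | Free | Common | Cut |
|---|---|---|---|
| Compound symmetry, ρ = .3 | .0467 | .0282 | 40% |
| Compound symmetry, ρ = .7 | .0200 | .0168 | 16% |
| AR(1), .5 | .0500 | .0308 | 38% |
| Random slope variance .05, intercept–slope correlation 0 | .0400 | .0309 | 23% |
| Random slope variance .5, correlation 0 | .1000 | .0909 | 9% |
| Random slope variance .05, correlation +.5 | .0400 | .0357 | 11% |
| Random slope variance .5, correlation +.5 | .1000 | .1000 | 0% |
| Random slope variance .05, correlation −.5 | .0400 | .0243 | 39% |
| Baseline SD .8 of later SDs, ρ = .5 | .0277 | .0242 | 12% |
| Baseline SD .5 of later SDs, ρ = .5 | .0242 | .0242 | 0% |

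These values are not bounds. Compound symmetry at ρ = .2 gives 46%. Equal-variance covariances matched to the plan's mean correlation of .5 and ε of about .6 give a median cut of 26%, with the middle half from 11% to 48%. With an unstructured covariance estimated at 15 per arm, simulation ranged from a 38% cut to a 5% loss.

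**4. Power, as an illustration only.** Suppose the 1-df slope test had power .50 with free intercepts. On 28 df its noncentrality would be 4.12. Dividing by .727 gives 5.66 and power .63. With dropout (20 df assumed) the noncentrality is 4.24; divided by .762 it gives power .61. Both figures assume a linear effect.

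**5. What the common-baseline slope estimates.** Expected slope per visit for a 1 SD effect, ρ = .5, complete data:

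| Course of effect | Free | Common |
|---|---|---|
| Linear | .500 | .500 |
| Appears at post-training and holds | .500 | .545 |
| Appears only at follow-up | .500 | .455 |
| Present at post-training, gone by follow-up | 0 | .091 |

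**6. If the arms truly differ at baseline.** Take a .3 SD gap at every visit and no effect. The common-baseline slope is .3 × 1.5/5.5 = .082 per visit, a false difference of .164 SD at follow-up, and type I error is about .07–.08.

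**The case against.** The planned model is a standard growth model, its interaction matches both hypotheses, and nothing in it is invalid. The study is a feasibility project already sized for a large effect. The alternative needs random allocation, which the supplied text does not describe, and it is biased if the arms truly differ at baseline. Training stops at week 4, so change need not be linear, and under non-linear change the two models estimate slightly different quantities. With an unstructured covariance and no small-sample correction, simulated type I error was .066–.072 with a common baseline against .055–.062 with a free one. The Kenward–Roger correction itself was not simulated.

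All of this stands. It makes the change conditional and optional, but does not remove the reason to consider it.

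Some stronger readings are tempting, and the documents do not support them:
- **The planned test is wrong.** It is not; it may only be less precise.
- **The plan's .50 would become .63.** The stated figure belongs to an omnibus test and cannot be converted directly to the slope test.
- **The gain has a known range.** No covariance is specified, so neither a typical value nor a ceiling follows from the text.
- **The intercept difference will be reported as efficacy.** The plan does not say so. With time centred at follow-up, the term would be a follow-up difference.

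**Conclusion.** The point holds as an optional efficiency gain. Both aims leave the baseline means free, and if allocation is random this can cost precision in the condition × time slope. The reference size is a 27% cut in slope variance, or about 24% with the assumed dropout. It rests on ρ = .5, compound symmetry, equal variances and equally spaced visits. Of these, only the correlation comes from the plan, and there only as a power input.

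The gain is about nil if spread widens markedly over time, or if intercept and slope are positively correlated with a large slope variance. It is 40% or more if correlations are low, and can be if they decay over time. An unstructured covariance at 15 per arm can turn it into a slight loss. The case is modest: the change is cheap and bears on the plan's acknowledged weak power for a medium effect, while power for the large effect is already about .90.

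**What to change.** State how participants are allocated. If allocation is random:

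- Code time 0 at baseline and drop the condition effect on the baseline intercept, keeping participants who have baseline data only. Alternatively, use baseline as a covariate with one post-baseline contrast named in advance.
- With the common-baseline model, keep the condition × time slope as the single efficacy test for each outcome, and do not read a baseline intercept difference as a treatment effect.
- State the covariance structure, whether slopes are random, and a small-sample correction such as Kenward–Roger.

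If allocation is not random, keep the free intercept.

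The cost is a few sentences in the analysis plan and no new data. The price is reliance on random allocation, a modest shift in what the slope summarises if change is not linear, and the need for the small-sample correction. The comparison of intercepts at baseline would also be given up.
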